**New Text /Subject Inclusion Criteria**

2. Men and nonpregnant, nonlactating women. Women must be either:
  - a. Naturally postmenopausal (as reported by the patient, defined as greater than 55 years and  $\geq 1$  year without menses, less than 55 years and  $\geq 1$  year without menses with follicle-stimulating hormone (FSH)  $\geq 40.0$  IU/L), or surgically sterile (including hysterectomy and/or bilateral oophorectomy, but not tubal ligation alone) or;
  - b. Women of childbearing potential must be willing to use 1 acceptable method of birth control. *The minimal requirement for adequate contraception should be started on Day 1, continuing during the study period, and for at least 30 days after the last dose of study drug.* Acceptable methods of birth control include: oral birth control medications; placement of an intrauterine device (IUD) with or without hormones; barrier methods including condom or occlusive cap with spermicidal foam or spermicidal jelly; vasectomized male partner who is the sole partner for this patient; or true abstinence (not including periodic abstinence such as calendar, ovulation, symptothermal, postovulation methods, or withdrawal).
  - c. There are no protocol-specific birth control requirements for men with partners who are able to become pregnant.

**Rationale**

Additional clarification to the start and duration of acceptable methods of birth control were required by Health Canada.

[name]  
Suite 150  
[name]

### 3. SECTION 8.5

#### New Text-New Section /Overdose/

There is no specific antidote for an overdose of bempedoic acid. Management of an overdose should be focused on the treatment of symptoms. These symptoms should be managed according to current standards of care with appropriate supportive measures. Also discontinuation of study drug should be considered.

#### Rationale

Information regarding overdose of bempedoic acid was required by Health Canada.

### 4. SECTION 10.2.2

#### Previous Text /Treatment Week 0 (Visit T1; Day 1)/

The patient will undergo the following assessments and procedures at (Visit T1)

- Concomitant and prohibited medication review (ongoing)
- Assess AEs (starting from signing of the informed consent document)
- Physical examination (PE)
- Weight
- 12-Lead electrocardiogram (ECG)
- Vital signs
- Clinical laboratory evaluations:
  - Hematology, blood chemistry, coagulation, and urinalysis
  - Basic fasting lipids (TC, calculated LDL-C, HDL-C, non-HDL-C, and TG)
  - apoB
  - HbA1C
  - hs-CRP
- Reserve sample

#### New Text /Treatment Week 0 (Visit T1; Day 1)/

The patient will undergo the following assessments and procedures at (Visit T1)

- Concomitant and prohibited medication review (ongoing)

[name]  
Suite 150  
[name]

- Assess AEs (starting from signing of the informed consent document)
- Physical examination (PE)
- Weight
- 12-Lead electrocardiogram (ECG)
- Vital signs
- Clinical laboratory evaluations:
  - Hematology, blood chemistry, coagulation, and urinalysis
  - *Urine pregnancy test (only for females of childbearing potential)*
  - Basic fasting lipids (TC, calculated LDL-C, HDL-C, non-HDL-C, and TG)
  - apoB
  - HbA1C
  - hs-CRP
  - Reserve sample

**Rationale**

Additional confirmation of pregnancy status of women of childbearing prior to randomization was required by Health Canada.

[name]  
Suite 150  
[name]

## 5. SECTION 11.1.6.1

### Previous Text /Laboratory Parameters (Safety), Table 5/

**Table 1: Clinical Laboratory Parameters (Safety)**

Clinical Laboratory Test	Clinical Laboratory Test

 
• Hematology
 
• Hematocrit (Hct)
 
• Hemoglobin (Hgb)
 
• Mean corpuscular hemoglobin (MCH)
 
• Mean corpuscular hemoglobin concentration (MCHC)
 
• Mean corpuscular volume (MCV)
 
• Platelet count
 
• Red blood (RBC) cell count
 
• White blood (WBC) cell count with differential (absolute and %)
 
	Blood Chemistry (serum, fasting) 
 
• Albumin (Alb)
 
• Alkaline phosphatase (Alk-P)
 
• Alanine aminotransferase (ALT; SGPT)
 
• Aspartate aminotransferase (AST; SGOT)
 
• Blood urea nitrogen (BUN)
 
• Calcium (Ca)
 
• Carbon dioxide (CO2)
 
• Chloride (Cl)
 
• Creatinine
 
• Creatine kinase (CK)
 
• Glucose
 
• Lactate dehydrogenase (LDH)
 
• Phosphorus
 
• Potassium (K)
 
• Sodium (Na)
 
• Total and direct bilirubin (TB)
 
• Total protein
 
• Uric acid
 

Urinalysis (Dipstick) 
 
• Clarity
 
• Bilirubin
 
• Color
 
• Glucose
 
• Ketones
 
• Leukocyte esterase
 
• Nitrate
 
• Occult blood
 
• pH
 
• Protein
 
• Specific gravity
 
• Urobilinogen
 
	

[name]  
 Suite 150  
 [name]

**Table 1: Clinical Laboratory Parameters (Safety) (Continued)**

Clinical Laboratory Test	Clinical Laboratory Test
Urinalysis (Microscopic)-only if urine dipstick abnormal 
 
• Bacteria
 
• Casts
 
• Crystals
 
• Epithelial cells
 
• Red blood cell (RBC)
 
• WBC
 
	Coagulation 
 
• Prothrombin time (PT)
 
• International normalized ration (INR)
 

Other Screening Labs 
 
• Hepatitis B surface antigen (HBsAg), hepatitis C virus (HCV)
 
• Serum pregnancy test (only for females of childbearing potential)
 
• Follicle-stimulating hormone (FSH; Females <55 years and >1 year without menses)
 
• Thyroid-stimulating hormone (TSH)
 
	Additional samples 
 
• Hemoglobin A1C (HbA1C)
 
• Reserve blood samples for potential future measurement of ETC-1002 safety or pharmacodynamic biomarkers
 
• PK sample
 
• Reserve genetic blood sample (optional)
 

[name]  
 Suite 150  
 [name]

**New Text /Laboratory Parameters (Safety), Table 5|**

**Table 2: Clinical Laboratory Parameters (Safety)**

Clinical Laboratory Test	Clinical Laboratory Test

 
• Hematology
 
• Hematocrit (Hct)
 
• Hemoglobin (Hgb)
 
• Mean corpuscular hemoglobin (MCH)
 
• Mean corpuscular hemoglobin concentration (MCHC)
 
• Mean corpuscular volume (MCV)
 
• Platelet count
 
• Red blood (RBC) cell count
 
• White blood (WBC) cell count with differential (absolute and %)
 
	Blood Chemistry (serum, fasting) 
 
• Albumin (Alb)
 
• Alkaline phosphatase (Alk-P)
 
• Alanine aminotransferase (ALT; SGPT)
 
• Aspartate aminotransferase (AST; SGOT)
 
• Blood urea nitrogen (BUN)
 
• Calcium (Ca)
 
• Carbon dioxide (CO2)
 
• Chloride (Cl)
 
• Creatinine
 
• Creatine kinase (CK)
 
• Glucose
 
• Lactate dehydrogenase (LDH)
 
• Phosphorus
 
• Potassium (K)
 
• Sodium (Na)
 
• Total and direct bilirubin (TB)
 
• Total protein
 
• Uric acid
 

Urinalysis (Dipstick) 
 
• Clarity
 
• Bilirubin
 
• Color
 
• Glucose
 
• Ketones
 
• Leukocyte esterase
 
• Nitrate
 
• Occult blood
 
• pH
 
• Protein
 
• Specific gravity
 
• Urobilinogen
 
	

[name]  
 Suite 150  
 [name]

**Table 2: Clinical Laboratory Parameters (Safety) (Continued)**

Clinical Laboratory Test	Clinical Laboratory Test
Urinalysis (Microscopic)-only if urine dipstick abnormal 
 
• Bacteria
 
• Casts
 
• Crystals
 
• Epithelial cells
 
• Red blood cell (RBC)
 
• WBC
 
	Coagulation 
 
• Prothrombin time (PT)
 
• International normalized ration (INR)
 

Other Screening Labs 
 
• Hepatitis B surface antigen (HBsAg), hepatitis C virus (HCV)
 
• Serum pregnancy test (only for females of childbearing potential)
 
• Urine pregnancy test prior to randomization (only for females of childbearing potential)
 
• Follicle-stimulating hormone (FSH); Females <55 years and >1 year without menses)
 
• Thyroid-stimulating hormone (TSH)
 
	Additional samples 
 
• Hemoglobin A1C (HbA1C)
 
• Reserve blood samples for potential future measurement of ETC-1002 safety or pharmacodynamic biomarkers
 
• PK sample
 
• Reserve genetic blood sample (optional)
 

**Rationale**

Additional confirmation of pregnancy status of women of childbearing potential prior to randomization was required by Health Canada.

[name]  
 Suite 150  
 [name]

## 6. APPENDIX 1

### Previous Text [Schedule of Events (Subject Visit Schedule)]

Visit	Screen	Treatment						
	S1 	T1	T2	T3	T4	T5	T6	T7 EOS 
Week	Wk -2	Wk 0	Wk 4	Wk 8	Wk 12	Wk 24	Wk 36	Wk 52
Procedure	Day -16 to -4	Day 1	Day 29±3	Day 57±3	Day 85±3	Day 169±7	Day 253±7	Day 365±7
Informed Consent	X							
Enrollment Criteria	X							
Demographics	X							
Medical History	X							
HeFH Status Determination	X							
Concomitant Medications	X	X	X	X	X	X	X	X
Adverse Event Recording		X	X	X	X	X	X	X
Physical Exam		X						X
Weight 	X	X	X	X	X	X	X	X
Height/BMI	X							
12-Lead ECG 		X						X
Vital Signs 	X	X	X	X	X	X	X	X
Serology 	X							
Serum Pregnancy and/or FSH 	X							
TSH	X							
Clinical Safety Labs 	X	X	X	X	X	X	X	X
Basic Fasting Lipids 	X	X	X	X	X	X	X	X
HbA 1C	X	X			X			X
10 mL reserve sample		X			X	X		X
apoB		X			X	X		X
hs-CRP		X			X	X		X
Diet and exercise counseling 	X	X	X	X	X	X	X	
Plasma PK					X	X		X
Establish Patient Eligibility		X						
Randomization		X						
IWRS Contact	X	X			X	X	X	X 
Double-blind Drug Dispensing 		X			X	X	X	
Drug Return/Compliance			X	X	X	X	X	X
Schedule next visit	X	X	X	X	X	X	X	X 

[name]  
 Suite 150  
 [name]

---

NOTE: For patients who withdraw from IMP treatment, but consent to be followed for safety assessments and return to clinic for these visit, the visits will occur according to the protocol schedule. Safety assessments should include clinical safety and basic lipid laboratories (except for apoB and hs-CRP), adverse events, PE, vital signs, and ECGs. For patients who withdraw from IMP treatment, but consent to be followed for safety assessments by phone, the telephone contacts will occur according the protocol schedule with information regarding current health status and to collect information on AEs (eg, recent procedures, hospitalizations, and if the patient has died, the cause of death). If a patient does not provide consent to be followed for safety assessments per the protocol (either by returning to clinic or by phone), Visit T7 will be considered the EOS/Early Withdrawal from study and no further visits will be scheduled.

 An optional visit approximately 1 week later MAY be completed if patient fails to meet a lipid entry criterion. If this optional visit is completed, the mean of lipid values from both visits will be used to determine eligibility.

 An optional visit between Visits S1 and T1 may be completed if the patient's DBP and/or SBP meet the exclusion criteria levels. Patients may randomize after blood pressure medications have been adjusted, the patients have been on stable doses of blood pressure medications for at least 2 weeks, and the repeat blood pressure values (DBP and/or SBP) do not meet exclusionary values. An optional visit between Visit S1 and T1 may be completed to determine eligibility if the patient's eGFR, ALT, AST, and/or TB meet exclusion criteria levels. If this optional visit is completed, the repeated value will be used to determine eligibility.

 All procedures will be completed for all patients at either End of Study (EOS) if completing the study or early withdrawal.

 Body weight will be measured in the morning while fasting, using consistent scales, after voiding, and without shoes and outerwear (eg, coats).

 Single 12-lead ECG will be collected prior to any blood sample collection.

 Vital signs will include DBP, SBP, and HR and will be collected prior to any blood sample collection. Patient will rest for 5 minutes prior to assessments

 Serology for HBsAg, HCV

 Pregnancy test completed in premenopausal women only. FSH test is completed in women <55 years old and >1 year without menses

 Clinical safety labs include hematology, blood chemistry, and urinalysis at all visits. Coagulation is included at Screening (Visit S1), Baseline (Visit T1), Week 12 (Visit T4), and at EOS (Visit T7). Please refer to [REDACTED] laboratory manual for detailed schedule of tests.

 Basic fasting lipids include total cholesterol, calculated LDL-C, HDL-C, non-HDL-C, and triglycerides. Repeat within 1 week if exceed protocol-specified criteria.

 Diet and exercise counseling per local and/or regional guidelines for the management of hyperlipidemia.

 IWRS contact at either an early withdrawal or an EOS visit to register study discontinuation visit date.

 Depending upon the length of time between visits, 1 or 2 bottles of study medication will be dispensed as instructed by IWRS. The bottle dispensed at Visit T1 will be returned to clinic at Visits T2 and T3 for evaluation of compliance and returned for continued use.

 If patient is discontinuing treatment and completing the EOS visit, but will be continuing in the study either by returning to clinic or by phone, continue to schedule study visits for the patient according to the protocol Schedule of Events

[name]

Suite 150

[name]

**New Text /Schedule of Events (Subject Visit Schedule)]**

Visit	Screen	Treatment						
	S1 	T1	T2	T3	T4	T5	T6	T7 EOS 
Week	Wk -2	Wk 0	Wk 4	Wk 8	Wk 12	Wk 24	Wk 36	Wk 52
Procedure	Day -16 to -4	Day 1	Day 29±3	Day 57±3	Day 85±3	Day 169±7	Day 253±7	Day 365±7
Informed Consent	X							
Enrollment Criteria	X							
Demographics	X							
Medical History	X							
HeFH Status Determination	X							
Concomitant Medications	X	X	X	X	X	X	X	X
Adverse Event Recording		X	X	X	X	X	X	X
Physical Exam		X						X
Weight 	X	X	X	X	X	X	X	X
Height/BMI	X							
12-Lead ECG 		X						X
Vital Signs 	X	X	X	X	X	X	X	X
Serology 	X							
Serum Pregnancy and/or FSH 	X							
Urine Pregnancy Test 		X						
TSH	X							
Clinical Safety Labs 	X	X	X	X	X	X	X	X
Basic Fasting Lipids 	X	X	X	X	X	X	X	X
HbA 1C	X	X			X			X
10 mL reserve sample		X			X	X		X
apoB		X			X	X		X
hs-CRP		X			X	X		X
Diet and exercise counseling 	X	X	X	X	X	X	X	
Plasma PK					X	X		X
Establish Patient Eligibility		X						
Randomization		X						
IWRS Contact	X	X			X	X	X	X 
Double-blind Drug Dispensing 		X			X	X	X	
Drug Return/Compliance			X	X	X	X	X	X
Schedule next visit	X	X	X	X	X	X	X	X 

[name]  
 Suite 150  
 [name]

---

NOTE: For patients who withdraw from IMP treatment, but consent to be followed for safety assessments and return to clinic for these visit, the visits will occur according to the protocol schedule. Safety assessments should include clinical safety and basic lipid laboratories (except for apoB and hs-CRP), adverse events, PE, vital signs, and ECGs. For patients who withdraw from IMP treatment, but consent to be followed for safety assessments by phone, the telephone contacts will occur according the protocol schedule with information regarding current health status and to collect information on AEs (eg, recent procedures, hospitalizations, and if the patient has died, the cause of death). If a patient does not provide consent to be followed for safety assessments per the protocol (either by returning to clinic or by phone), Visit T7 will be considered the EOS/Early Withdrawal from study and no further visits will be scheduled.

 An optional visit approximately 1 week later MAY be completed if patient fails to meet a lipid entry criterion. If this optional visit is completed, the mean of lipid values from both visits will be used to determine eligibility.

 An optional visit between Visits S1 and T1 may be completed if the patient's DBP and/or SBP meet the exclusion criteria levels. Patients may randomize after blood pressure medications have been adjusted, the patients have been on stable doses of blood pressure medications for at least 2 weeks, and the repeat blood pressure values (DBP and/or SBP) do not meet exclusionary values. An optional visit between Visit S1 and T1 may be completed to determine eligibility if the patient's eGFR, ALT, AST, and/or TB meet exclusion criteria levels. If this optional visit is completed, the repeated value will be used to determine eligibility.

 All procedures will be completed for all patients at either End of Study (EOS) if completing the study or early withdrawal.

 Body weight will be measured in the morning while fasting, using consistent scales, after voiding, and without shoes and outerwear (eg, coats).

 Single 12-lead ECG will be collected prior to any blood sample collection.

 Vital signs will include DBP, SBP, and HR and will be collected prior to any blood sample collection. Patient will rest for 5 minutes prior to assessments

 Serology for HBsAg, HCV

 Serum and urine pregnancy tests completed in premenopausal women or women of childbearing potential only. FSH test is completed in women <55 years old and >1 year without menses

 Clinical safety labs include hematology, blood chemistry, and urinalysis at all visits. Coagulation is included at Screening (Visit S1), Baseline (Visit T1), Week 12 (Visit T4), and at EOS (Visit T7). Please refer to [REDACTED] laboratory manual for detailed schedule of tests.

 Basic fasting lipids include total cholesterol, calculated LDL-C, HDL-C, non-HDL-C, and triglycerides. Repeat within 1 week if exceed protocol-specified criteria.

 Diet and exercise counseling per local and/or regional guidelines for the management of hyperlipidemia.

 IWRS contact at either an early withdrawal or an EOS visit to register study discontinuation visit date.

 Depending upon the length of time between visits, 1 or 2 bottles of study medication will be dispensed as instructed by IWRS. The bottle dispensed at Visit T1 will be returned to clinic at Visits T2 and T3 for evaluation of compliance and returned for continued use.

 If patient is discontinuing treatment and completing the EOS visit, but will be continuing in the study either by returning to clinic or by phone, continue to schedule study visits for the patient according to the protocol Schedule of Events

[name]

Suite 150

[name]

**1002-040 Protocol Version: Amendment #2**

**Administrative Change Letter:**

**1002-040-Am2-CA-01-Admin**

**Canadian Sites Only**

**Rationale**

Additional confirmation of pregnancy status of women of childbearing prior to randomization was required by Health Canada.

[name]  
Suite 150  
[name]

HDL-C	High-density lipoprotein cholesterol
HeFH	Heterozygous familial hypercholesterolemia
Hgb	Hemoglobin
HIV	Human immunodeficiency virus
HMG-CoA	3-hydroxy-3-methylglutaryl coenzyme A
hsCRP	High-sensitivity C-reactive protein
IB	Investigator's Brochure
ICD	Informed Consent Document
ICH	International Conference on Harmonisation
IEC	Independent Ethics Committee
IMP	Investigational medicinal product
IND	Investigational New Drug Application
INR	International normalized ratio
IMP	Investigational Medicinal product
IRB	Institutional Review Board
ITT	Intention-to-treat
IWRS	Interactive web response system
K	Potassium
LDH	Lactate dehydrogenase
LDL-C	Low-density lipoprotein cholesterol
LDLR	LDL receptor
LFT	Liver function test
LMT	Lipid Modifying Therapy
LPLV	Last patient last visit
LSM	Least square mean
MACE	Major adverse cardiac event
MCH	Mean corpuscular hemoglobin
MCHC	Mean corpuscular hemoglobin concentration
MCV	Mean corpuscular volume
MDRD	Modification of diet in renal disease
MED ID	Medication identification
MI	Myocardial infarction

Abbreviation or Specialist Term	Explanation
MRI	Magnetic resonance imaging
Na	Sodium
NCEP	National Cholesterol Education Program
NOAEL	No-observed-adverse-effect level
non-HDL-C	Non-high-density lipoprotein cholesterol
NYHA	New York Heart Association
PCI	Percutaneous coronary intervention
PE	Physical exam
PK	Pharmacokinetic(s)
PMM	Pattern mixture model
PT	Prothrombin time
RBC	Red blood cell
SAE	Serious adverse event
SAP	Statistical Analysis Plan
SBP	Systolic blood pressure
SE	Standard error
SGOT	Serum glutamic oxaloacetic transaminase
SGPT	Serum glutamic pyruvic transaminase
SOP	Standard operating procedures
SP	Safety population
SUSARS	Suspected and unexpected serious adverse reactions
T2DM	Type 2 diabetes mellitus
TB	Total bilirubin
TC	Total cholesterol
TEAE	Treatment-emergent adverse event
TG	Triglycerides
TIA	Transient ischemic attack
TSH	Thyroid-stimulating hormone
TQT	Thorough QT/QTc
ULN	Upper limit of normal
US	United States
WBC	White blood cell
WHO	World Health Organization

2 Introduction

The purpose of this document is to describe the statistical methods, data derivations and data summaries to be employed in ETC-1002-040. The preparation of this statistical analysis plan (SAP) has been based on International Conference on Harmonisation (ICH) E3 and E9 Guidelines and in reference to Protocol ETC-1002-040 (Protocol Amendment 5, 10 May 2017).

The SAP will supersede the protocol in the event of any differences between the two documents in the plans for data analysis, and the protocol will be amended if appropriate. The SAP will be included as an appendix in the clinical study report for this protocol.

3 Study Objectives and Endpoints

3.1 Objectives

The primary objective for this study is to evaluate the long-term safety and tolerability of ETC-1002 (bempedoic acid) versus placebo in high cardiovascular (CV) risk patients with hyperlipidemia (with underlying heterozygous familial hypercholesterolemia [HeFH] and/or atherosclerotic cardiovascular diseases [ASCVD]) who are not adequately controlled with their maximally tolerated lipid-modifying therapy.

The secondary objective is to assess the efficacy as the percent change from baseline to Week 12 in low-density lipoprotein cholesterol (LDL-C). This is the primary efficacy endpoint.

The tertiary objectives are:

- To assess percent change from baseline to Week 24 and to Week 52 in LDL-C in patients who do not receive adjunctive lipid lowering therapy.
- To assess high-density lipoprotein cholesterol (HDL-C), non-HDL-C, total cholesterol (TC), and triglycerides (TG) values at Week 12, 24 and 52.
- To assess apolipoprotein B (apoB) and high-sensitivity C reactive protein (hsCRP) values at Week 12, 24, and 52.

3.2 Primary Safety Endpoints

The primary safety endpoint for this study is general safety, which includes adverse events (AEs), clinical safety laboratories, physical examinations (PEs), vital signs, and electrocardiogram (ECGs).

3.2.1 Adverse Events

The evaluation of AEs will include only incidence of treatment-emergent AEs (TEAEs), defined as AEs that begin or worsen after the first dose of IMP until 30 days after last dose of IMP. Clinical endpoints will be collected and adjudicated by an independent

Confidential

Page 7 of 33

Clinical Events Committee (CEC). Clinical endpoints will also be reported as SAEs. Adverse events of special interest (AESI) will further be examined (See Section 5.4.2 for more information).

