#### **10.2.8. Treatment Week 52 (Visit T7; ± 7 days)**

Patients will undergo the following assessments and procedures at Week 52 (Visit T7), when completing an End of Study (EOS) visit, withdrawing from study (early withdrawal), or withdrawing from IMP treatment:

Patients will undergo the following assessments and procedures at Week 52 (Visit T7):

- Concomitant and prohibited medication review (ongoing)
- Assess AEs, including muscle-related AEs (ongoing)
- PE
- Weight
- 12-Lead ECG
- Vital signs
- Clinical laboratory evaluations:
  - Hematology, blood chemistry, and urinalysis
  - Basic fasting lipids (TC, calculated LDL-C, HDL-C, non-HDL-C, and TG)
  - apoB
  - HbA1C
  - hs-CRP
  - PK sample (*patients randomized after Protocol Amendment 3 and subsequent amendments are excluded from PK sampling*)
  - Reserve sample
- Return of IMP; assessment and recording of IMP compliance
- Complete study status in IWRS (ie, early withdrawal or completed study)
- *Review and offer the open-label extension study (Study 1002-050) to the patient*

Note: For patients who withdraw from IMP treatment:

- *Capture the reason for withdrawing from IMP treatment and record on the eCRF*
- Determine whether the patient will or will not consent for follow-up visits through study completion
- If the patient provides consent to continue to be followed for safety assessments per the protocol visit schedule, schedule follow-up visits as they would have occurred if the patient were continuing in the study and complete the visit required procedures listed in the appropriate visit specific section within **Section 10** and **Appendix 1**. No further IMP will be dispensed for patients who withdraw from IMP treatment.
- If the patient does not provide consent to be followed for safety assessments per the protocol (either by returning to clinic or by phone), this visit (Visit T7) will be considered the EOS/Early Withdrawal from study visit and no further visits will be scheduled.

Note: If this visit is being conducted at the site for patients who have consented to be followed for safety assessments, *including basic fasting lipids*, after withdrawing from

IMP treatment, all assessments except for those procedures pertaining to apoB, hs-CRP, PK samples, reserve samples, and IMP (IMP dispensing, IMP compliance, IMP accountability) management should be completed.

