### **11.2.3. Reporting**

All AEs occurring during the course of the study (starting from signing informed consent to study completion) will be collected on the AE eCRF. Patients should be instructed to report any AE that they experience to the Investigator. Beginning with Visit S1 (Week -2), Investigators should make an assessment for AEs at each visit and record the event on the appropriate AE eCRF.

Wherever possible, a specific disease or syndrome rather than individual associated signs and symptoms should be identified by the Investigator and recorded on the eCRF. However, if an observed or reported sign or symptom is not considered a component of a specific disease or syndrome by the Investigator, it should be recorded as a separate AE on the eCRF. Additionally, the condition that led to a medical or surgical procedure (eg, surgery, endoscopy, tooth extraction, transfusion) should be recorded as an AE, not the procedure.

Any medical condition already present at screening or baseline should not be reported as an AE unless the medical condition or signs or symptoms present at baseline changes in severity or seriousness at any time during the study. In this case, it should be reported as an AE.

Clinically significant abnormal laboratory or other examination (eg, ECG) findings that are detected during the study or are present at baseline and significantly worsen during the study should be reported as AEs. The Investigator will exercise his or her medical and scientific judgment in deciding whether an abnormal laboratory finding or other abnormal assessment is clinically significant. Significant abnormal laboratory values occurring during the clinical study will be followed until repeat tests return to normal, stabilize, or are no longer clinically significant. Any abnormal test that is determined to be an error does not require reporting as an AE.

Each AE is to be evaluated for duration, severity, seriousness, and causal relationship to the investigational drug. For each AE, the following information will be recorded:

- Description of the event (eg, headache)
- Date of onset
- Date of resolution (or that the event is continuing)
- Action taken as a result of the event
- Seriousness of the event
- Severity of the event
- Outcome of the event
- Investigator's assessment of relationship to study drug.

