### **11.3. Reporting Serious Adverse Events**

*All SAEs, regardless of relationship to study drug, occurring from the time of informed consent until 30 days following study completion or study discontinuation, must be reported by the Principal Investigator or designee to [REDACTED] Medical and Safety Services within 24 hours of the Principal Investigator or the clinical site becoming aware of the occurrence. For most patients this will be 30 days following their Week 52 (Visit T7) visit. All SAEs that the Investigator considers related to study drug that occur after the 30-day follow-up of the study period must be reported to the Sponsor.*

To report the SAE, complete the provided SAE form and fax it to [REDACTED] Medical and Safety Services within 24 hours of becoming aware of the occurrence. Regional fax numbers will be listed on the bottom the provided SAE form. If you are unable to fax the SAE form or if you have questions, please call [REDACTED] Medical and Safety Services for assistance. [REDACTED] Safety personnel are available for SAE reporting on a 24-hour basis. Incoming reports are reviewed during normal business hours.

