5.2.9 IMP Exposure and Compliance

The length of exposure to IMP (ETC-1002 or placebo) will be calculated as the number of days from the first dose of double-blind IMP to the last dose of double-blind IMP, regardless if the patient missed one or more doses of IMP. Length of exposure will be summarized by treatment group using descriptive statistics for the safety population.

The number and percentage of patients who were compliant with taking IMP will be summarized by treatment group for the safety population for the following categories 0- $<80\%$; $\geq 80\%$.

Overall compliance will be calculated as: $100 * (\text{Total Number of Tablets Dispensed} - \text{Total Number of Tablets Returned}) / (\text{Treatment Duration in Days})$. The IMP administration and compliance data, including reasons for poor compliance, if noted in CRF will be listed for each patient.

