5.4.5 Clinical Cardiovascular Endpoints

Clinical cardiovascular endpoints will be monitored and adjudicated by an independent blinded expert CEC for this study and other ongoing studies the ETC-1002 program. Adjudicated clinical endpoints that are treatment-emergent will be summarized by event type and treatment group. All events will be provided in a listing. Additional details regarding clinical endpoints and clinical endpoint definitions will be included in CEC charter.

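### The treatment-emergent window runs 30 days past the last double-blind dose with no cut-off at extension entry, so serious events on open-label drug could be tabulated under placebo

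*SAP*

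**What the plan says.** SAP 3.2.1 defines treatment-emergent events as "AEs that begin or worsen after the first dose of IMP until 30 days after last dose of IMP". SAP 5.2.9 shows that IMP means blinded study drug: exposure is "the number of days from the first dose of double-blind IMP to the last dose of double-blind IMP". The protocol's own definition (11.2.7) has no end date, and the SAP takes precedence for analysis (SAP 2).

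At Week 52, Protocol 10.2.8 tells the site to "Review and offer the open-label extension study (Study 1002-050) to the patient". The Amendment 5 summary of changes links this step to patients finishing the study while on IMP, whose last blinded dose therefore falls at about Week 52.

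Collection continues past that visit. Serious events "occurring from the time of informed consent until 30 days following study completion or study discontinuation, must be reported", and Protocol 11.3 adds: "For most patients this will be 30 days following their Week 52 (Visit T7) visit". They are recorded on the eCRF. Protocol 11.3.2 sets the same 30-day period for deaths. Other adverse events are collected only "starting from signing informed consent to study completion" (Protocol 11.2.3).

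Safety tables group patients by the treatment received (SAP 5.2.1.1 and 5.4). The same flag governs the cardiovascular endpoints: "Adjudicated clinical endpoints that are treatment-emergent will be summarized by event type and treatment group" (SAP 5.4.5). The SAP does not mention Study 1002-050.

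**The concern.** For a patient who completes on IMP, the 30-day tail falls almost entirely after the visit at which the extension is offered. Serious events and deaths in that tail are still reported to this study, and the SAP has no rule for drug taken after the blinded phase. A placebo completer who starts open-label ETC-1002 and has a serious event two weeks later would meet the treatment-emergent definition and be counted under placebo.

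The error would run one way. A former ETC-1002 patient's event stays with ETC-1002, while a former placebo patient's event on active drug is credited to placebo. Safety against placebo is the primary objective, and the outputs exposed are those with the smallest counts: serious events, deaths and adjudicated endpoints.

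**Working it through.** **Inputs from the documents.** 650 placebo and 1300 ETC-1002 patients; dropout 7.5% at 6 months and 10.0% at 12 months; lowest planning rate 0.5% (SAP 4.4). Tail of 30 days (SAP 3.2.1).

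**Assumptions, not in the documents.** The extension gives ETC-1002; dosing starts promptly after Week 52; 50% to 90% of placebo completers enter.

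**1. The plan's own figures.**
- Exposure: 650 × 0.925 = 601.25 and 650 × 0.90 = 585; 1300 × 0.925 = 1202.5 and 1300 × 0.90 = 1170. These match the stated 601, 585, 1,202 and 1,170.
- Intervals: RR × exp(±1.96 × √(1/a − 1/1300 + 1/b − 1/650)), with a and b the expected ETC-1002 and placebo event counts, gives (0.26, 3.77), (0.60, 6.72), (0.79, 1.27) and (1.62, 2.48). These match the SAP's table after rounding.

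The sample-size section is not in question. It supplies the 585 completers and the yardstick for precision.

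**2. Placebo time in the treatment-emergent window.**
- Mean fraction retained, with linear dropout within each half-year: 0.5 × (1 + 0.925)/2 + 0.5 × (0.925 + 0.90)/2 = 0.9375.
- Blinded phase: 650 × 0.9375 = 609.4 patient-years.
- 30-day tail for all: 650 × 30/365.25 = 53.4 patient-years.
- Total: 662.8 patient-years.

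**3. Overlap with open-label dosing:** 585 × uptake × 30/365.25.
- 50% uptake: 24.0 patient-years; f = 24.0/662.8 = 3.6%.
- 90% uptake: 43.2 patient-years; f = 43.2/662.8 = 6.5%.
- Ceiling at 100%: 48.0 patient-years; f = 7.2%.

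**4. Effect on the comparison.** Let the event rate be λ on placebo and RR × λ on drug, constant over time. The tabulated placebo rate is then (1 − f)λ + f × RR × λ = λ(1 + f(RR − 1)), so the observed RR = RR/(1 + f(RR − 1)).
- True RR 2.0: 2/1.036 = 1.93 and 2/1.065 = 1.88.
- True RR 1.5: 1.5/1.018 = 1.47 and 1.5/1.033 = 1.45.
- True RR 1.0: 1.0 at any f.

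**5. Rare events.** At the 0.5% planning rate, 650 × 0.005 = 3.25 placebo patients are expected. One misplaced case would raise that count by about 31% (1/3.25).

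**The case against.** The strongest answer is that the harm depends on a study we cannot see. The documents do not give the extension's drug, eligibility, start of dosing or uptake, and do not say whether a serious event after entry goes to this study, to Study 1002-050 or to both. If dosing starts more than 30 days after the last blinded dose, or if reporting transfers at entry, there is no overlap. This stands as a limit on certainty. It does not remove the gap, because Protocol 11.3 as written requires reporting here and exempts nobody who rolls over.

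Second, a reader might count the misplaced events and take that count as the damage. At an assumed 10 to 15 serious events per 100 patient-years, 24.0 × 0.10 = 2.4 to 43.2 × 0.15 = 6.5 events would fall in the overlap. That is not the bias. If the same rate applies on placebo, those events would be expected there anyway and the placebo rate is unchanged; only an excess caused by the drug distorts the contrast. Even the count is an upper bound on added patients, since SAP 5.4.1 reports patient incidence and the overview counts a patient at most once per category.

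Third, reach is narrow. Scheduled laboratory, vital-sign and ECG data end at Week 52, and new non-serious events are not collected afterwards. Worsening of an event still ongoing at completion is a small extra route. SAP 5.4.1 and 5.4.5 also list all events, so late ones could be inspected, although no extension flag is specified.

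Finally, SAP Appendix 1 lacks the protocol's row for offering the extension. A reader might infer a decision to ignore it. The documents do not support that: the appendix also lacks the Amendment 5 reserve-sample footnote, so it looks like a schedule carried over from before that amendment.

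**Conclusion.** The gap in the rule is certain: the SAP has no cut-off at extension entry, and serious events and deaths are collected into the same 30 days. Misattribution is conditional on the extension giving ETC-1002 and on dosing starting inside the window.

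Given both conditions and the assumed uptake, the bias is toward no difference and modest. A fall in the observed relative risk from 2.0 to between 1.93 and 1.88 is small beside the SAP's planned intervals at that value, (1.6, 2.5) for common events and (0.6, 6.7) for rare ones. A reader might infer that the overlap would make the two arms look alike on serious events; the arithmetic does not support that. The practical exposure is in rare serious events, deaths and adjudicated endpoints, where a single case under the wrong arm can be seen in the table. The change is worth making because it is cheap and removes an avoidable question about the primary comparison.

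**What to change.** In SAP 3.2.1, end the treatment-emergent window at the earlier of (a) 30 days after the last double-blind dose and (b) the day before the first dose in Study 1002-050. Apply the same end date to the serious and fatal event tables in 5.4.1 and to the adjudicated endpoints in 5.4.5. List events from the first extension dose onward separately, and keep the fixed 30-day window as a sensitivity summary.

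The cost is a short SAP edit and a merge of the first-dose date from Study 1002-050. The price in information is slightly shorter post-dose follow-up for patients who roll over: some early events after rollover may reflect blinded treatment, and follow-up length then depends on the choice to enter the extension. The sensitivity summary covers both points.
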